Protocol Addendum

September 22, 2016

This document is the required IRB/EC notification about ISCHEMIA protocol modifications.

Summary:

This document is an addendum to the ISCHEMIA protocol describing changes to:

- 1. Minimum and average duration of follow-up for randomized participants, and
- 2. Number of randomized participants planned for ISCHEMIA and ISCHEMIA-CKD trials
- 3. The timeframe for serum creatinine measurement at enrollment for participants on dialysis

The ISCHEMIA Data Safety and Monitoring Board and NHLBI approved these changes. These changes will not have any effect on participant safety or the risk-to-benefit ratio of study participation.

Site IRBs/ECs should determine whether the sample size and minimum follow-up duration in the informed consent, if referenced, need to be changed. Any changes to the ISCHEMIA informed consent forms will require IRB/EC submission, review and approval. Sites are required to send copies of the IRB/EC approval letter and informed consent to the ISCHEMIA Clinical Coordinating Center when received.

1. Minimum and average duration of follow-up for randomized participants

Based on the ISCHEMIA and ISCHEMIA-CKD trials' current observed randomization trajectory, enrollment and last follow-up dates will be extended beyond the original projected dates. Therefore, to achieve objectives within timelines allotted by the Sponsor, the minimum follow-up duration for randomized participants will be approximately 12-18 months (reduced from 18-24 months), with the average follow-up estimated to be approximately 3 years (reduced from 4 years).

- 2. Number of randomized participants projected for ISCHEMIA and ISCHEMIA-CKD trials, modified to achieve the trials' objectives within timelines allotted by the Sponsor, NHLBI.
 - 2.1. For ISCHEMIA, approximately 5,000 to 6,000 participants are projected to be randomized; a reduction from the original planned 8,000 randomized participants.

The original planned sample size of approximately 8,000 participants afforded robust power (over 90%) to detect a 15% reduction in the rate of the primary endpoint of cardiovascular (CV) death or myocardial infarction (MI). It was more than three times the size of all prior strategy trials of cardiac catheterization/prompt revascularization vs. medical therapy only in both stable ischemic heart disease and non-ST elevation acute coronary syndrome (ACS, different population from ISCHEMIA).

With a sample size of 5,000 participants followed for an average of 3 years (minimum of approximately 12 months), the trial will have \geq 83% power to detect an 18% reduction (from 20% to 16.4%) in the 4-year rate of the primary composite endpoint in participants randomized to an invasive strategy (INV) as compared with a conservative strategy (CON), assuming a 4-year rate of the primary endpoint of 20% in the CON group. The true hazard ratio can be estimated to within a multiplicative margin of error of 1.15 with 0.95 confidence.

Based on the trial's current observed randomization trajectory, the sample size was reduced to achieve the enrollment objectives within timelines allotted by the Sponsor, while maintaining a high level of statistical precision and adequate power to achieve original objectives. The projections are estimates based on randomization rates. If these rates increase, the number of randomized participants may exceed 6000. As expected the number of **enrolled** patients exceeds the number randomized due to failure to confirm eligibility in all enrolled participants.

2.2. ISCHEMIA-CKD ancillary trial, approximately 500 to 700 participants are projected to be randomized, a reduction from the original planned 1,000 participants.

The original planned sample size of approximately 1,000 participants was designed to provide 80-95% power to compare the primary endpoint across the two randomized groups assuming the 4-year cumulative rate of the primary composite endpoint is 50%-70% in participants randomized to the CON strategy and is less by a factor of 15% to 19% (relative reduction) in participants randomized to the INV strategy.

Since the initial design, several sources of evidence reinforced the primary event rate assumed for the trial. Although none of the studies report the exact information needed for this trial, we have assumed a conservative death or MI event rate of 60% to 75%. Given the high risk of the CKD trial cohort, it is reasonable to power for a larger relative risk reduction than our previous assumption.

With a final sample size of 500 participants, followed for an average of 3 years (minimum of approximately 18 months), the trial will have power of >81% for detecting a 23%-27% reduction in the 4-year rate of the primary endpoint, assuming a cumulative 4-year event rate of 60% to 75% in the CON group.

Based on the trial's current observed randomization trajectory, the sample size was reduced to achieve the enrollment objectives within timelines allotted by the Sponsor, while maintaining a high level of statistical precision and adequate power to achieve original objectives. The projections are estimates based on randomization rates. If these rates increase, the number of randomized participants may exceed 700. As expected the number of **enrolled** patients exceeds the number randomized due to failure to confirm eligibility in all enrolled participants.

3. The timeframe for serum creatinine measurement at enrollment for participants on dialysis

The protocol requires serum creatinine measurement within 90 days prior to enrollment. This is to ensure that the renal function of enrolled participants is current. However, this is not applicable to participants who are already on dialysis, as serum creatinine is not needed in these participants for trial purposes.

1. INTRODUCTION

The purpose of this Statistical Analysis Plan is to outline the types of analyses and data presentations that will be used to answer the study objectives outlined in the protocol, and to explain in detail how the data will be handled and analyzed. It describes the study's planned final analysis for presentation in the primary and selected secondary manuscripts, planned interim endpoint comparisons by treatment performed for the Data & Safety and Monitoring Board (DSMB), and various additional planned interim analyses performed for operational monitoring and quality assurance.

2. STUDY DESIGN

ISCHEMIA is an international comparative effectiveness study. Participants are recruited following clinically indicated stress testing and randomized in a 1:1 fashion to an invasive or conservative strategy.

3. STUDY OBJECTIVES

The primary aim of ISCHEMIA is to determine for participants with stable ischemic heart disease (SIHD) and at least moderate ischemia by non-invasive assessment whether an initial invasive (INV) strategy of cardiac catheterization and feasible optimal revascularization in addition to optimal medical therapy

(OMT) will reduce adverse cardiovascular events when compared with an initial conservative (CON) strategy of OMT alone with catheterization and revascularization reserved for failure of OMT.

The primary endpoint is the composite of cardiovascular (CV) death, non-fatal myocardial infarction (MI), and hospitalization for unstable angina, heart failure, or resuscitated cardiac arrest. This 5-item composite endpoint was the primary endpoint in the NHLBI grant application in 2010 but then was listed as a secondary endpoint in the original protocol. The primary endpoint in the original protocol was the 2-item composite of CV death or MI. The primary endpoint was changed back to the 5-item composite in June 2017 after following a protocol-defined process to re-estimate power based on blinded review of accumulating study data and finding that power for the original 2-item primary composite endpoint was lower than originally expected (see Section 11.5 and the SAP Appendix for Contingency Plan for Insufficient Primary Endpoint Events for details; this was done with approval of the Director of the NHLBI).

The incidence of the 2-item composite of CV death or MI will be compared between the INV and CON strategies and will be the major secondary analysis of the ISCHEMIA trial.

Other secondary objectives include comparing the incidence of the following between the INV and CON strategies:

1. Inclusion of stroke with other components of the primary and the major secondary endpoints to assess “Net Clinical Benefit” as follows:

- a. Cardiovascular events including CV death, non-fatal MI, and hospitalization for unstable angina, hospitalization for heart failure, resuscitated cardiac arrest or stroke
- b. CV death, non-fatal MI or stroke

2. Individual components of the primary composite endpoint

3. Stroke

4. All-cause death

Another secondary objective is to determine whether an INV strategy is more effective than a CON strategy in improving angina control, as assessed by the Seattle Angina Questionnaire (SAQ) Angina Frequency scale, and disease-specific quality of life, as assessed by the SAQ Quality of Life scale.

Finally, health resource utilization, cost, and cost-effectiveness will also be compared between the two randomized strategies. Separate Statistical Analysis Plans for secondary manuscripts will be developed for the analysis of disease-specific quality of life data.

4. SAMPLE SIZE CONSIDERATIONS

In designing ISCHEMIA, it was originally estimated that a study with 8,000 participants followed for an average of 3.7 years would have 90% power to detect a 15% relative reduction in the 4-year rate of the primary endpoint in participants randomized to an invasive strategy as compared with a conservative strategy, assuming a 4-year rate of the primary endpoint of 20% in the conservative strategy group. A

modest relative reduction was used in power calculations in light of ISCHEMIA's strategy trial design which includes participants without prior known anatomy and the expectation that not all participants in the target population will be suitable for revascularization or benefit equally from an invasive strategy. The modest between-group difference was also intended to account for attenuation of the treatment effect by non-adherence to the randomized treatment strategy. The between-group difference would be larger if a high adherence rate was expected. Participants in the conservative group who undergo catheterization for unacceptable angina despite maximal OMT are not considered non-adherent (because the conservative strategy includes performance of catheterization after OMT failure) but such catheterizations may reduce power for the primary endpoint if they, or the revascularizations that the catheterizations lead to, prevent the occurrence of primary endpoint events. Such attenuation was incorporated in sample size calculations by specifying a between-group difference that is smaller than it would be hypothetically if catheterization and revascularization was never performed in the conservative strategy.

Based on the trial's observed monthly randomization numbers, an analysis performed in August 2015 revealed that approximately 4,400 participants were projected to be randomized by the end of the trial's original planned enrollment period (October 2012 – June 2017). In response, the study's leadership proposed extending enrollment for 6 months beyond the original projected last enrollment date (from June 2017 to December 2017) and extending the follow-up period for 6 months beyond the original projected last follow-up date (from June 2018 to December 2018). Study leadership requested a reduction in sample size on the grounds that the original target of 8,000 was unlikely to be met and that the study would still be adequately powered albeit for a larger effect size. In August 2016, study leadership received permission from NHLBI to continue the study with a reduced sample size target of 5,000 randomized participants.

To ensure an adequate number of endpoint events for the primary analysis, the initial ISCHEMIA protocol (version 1.0 dated January 18, 2012) included a contingency plan to allow changing the primary endpoint from the 2-item to the 5-item endpoint after trial initiation by following a process with safeguards incorporated to protect against bias and inflation of the type-I error rate (see Section 11.5 and SAP Appendix for Contingency Plan for Insufficient Primary Endpoint Events for details). At various points in the trial, the primary endpoint event rate and statistical power were re-estimated using updated assumptions derived from blinded pooled analyses (not by treatment group) of the accumulating trial data. In May 2017, an independent panel was convened by NHLBI for the purpose of reviewing relevant blinded aggregate study data and power calculations and advising the NHLBI director and study leadership about possible design modifications. After reviewing updated power and precision estimates, the panel recommended reverting to the grant-funded 5-component primary endpoint and extending follow-up to the maximum duration feasible in order to increase power. The panel's recommendation was approved by NHLBI and study leadership in June 2017.

In February 2018, power was re-estimated for the study's revised primary endpoint (5-item composite) using updated event rate assumptions and assuming that participants would be followed until June 2019. The final sample size of 5,179 participants was estimated to provide 80% power to detect an 18.5% relative reduction in the 4-year rate of the 5-item primary composite endpoint. This sample size would also allow estimation of the hazard ratio to within a multiplicative margin of error of 1.17 with 0.95 confidence.

5. RANDOMIZATION METHODOLOGY

Enrollment and randomization is accomplished by contact with the interactive web/voice randomization system (IXRS). When a participant meeting site-determined clinical and stress imaging criteria has provided informed consent, the study coordinator or investigator at the site will call or log into the IXRS to receive a participant identification number. At this point the participant is registered as enrolled. In order to randomize the participant, the study coordinator or investigator must call or log into the IXRS a second time. Participants meeting all clinical and site inclusion criteria are then randomized to either the INV or CON strategy and registered as randomized. Ischemia severity is determined by sites and is reported according to independent core laboratory review. Randomization information, including the randomized treatment assignment, is transmitted to the participant's electronic case book within the electronic data capture (EDC) system.

The original randomization scheme for ISCHEMIA was a permuted block design with stratification by enrolling site to balance the distribution of treatment assignments within the sites. The block sizes for each site were chosen at random to reduce the likelihood of an investigator predicting the next treatment group assignment. Beginning in March 2014, ISCHEMIA's randomization system was modified to facilitate enrollment of participants into the ISCHEMIA-CKD ancillary trial. The randomization lists that were originally generated for ISCHEMIA were subsequently used for randomizing both ISCHEMIA and ISCHEMIA-CKD participants together. Assigned participant identification numbers are different depending on whether the participant was enrolled in ISCHEMIA-CKD or the ISCHEMIA main trial. Details about distinguishing between ISCHEMIA-CKD and ISCHEMIA main trial participants can be found in the SAP Appendix for Definitions and Reporting Conventions.

6. PARTICIPANT POPULATIONS

All major treatment comparisons between the randomized groups in this trial will be performed according to the principle of "intention-to-treat"; that is, participants will be analyzed according to the treatment group to which participants were randomized, regardless of subsequent non-adherence to protocol. Participant populations of interest are described below.

6.1. Intention-to-treat population

The intention-to-treat (ITT) population will include all participants who receive a randomized treatment assignment, including those who are later determined not to meet trial eligibility criteria, unless the randomization was an unintentional administrative error, as determined by the Clinical Coordinating Center (CCC) in conjunction with the Statistical and Data Coordinating Center (SDCC) and National Heart, Lung, and Blood Institute (NHLBI) program officers. Of note, the ITT population will include participants who are randomized prior to or in absence of core-lab determination of ischemia regardless of subsequent core lab findings. Similarly, participants randomized prior to or in absence of a study CCTA will be included regardless of any subsequent determination of left main disease or no obstructive disease.

6.2. Protocol Version 2.0 population

The Protocol Version 2.0 population will include all randomized participants except for those with a documented violation of trial eligibility criteria and those with prior CABG enrolled under Protocol

Version 1.0. In general, determination of eligibility will be based on the version of the protocol under which the participant was randomized. Participants with prior CABG enrolled under Version 1.0 are excluded in order to better reflect the final Version 2.0 target population which excludes prior CABG participants unless their coronary anatomy is known to be suitable for PCI or repeat CABG. Unlike the ITT population, the Protocol Version 2.0 population will exclude participants accidentally randomized despite having left main disease or no obstructive disease on study CCTA. For determining eligibility, the presence of at least moderate ischemia will be based on the local site interpretation rather than the core lab interpretation. Presence of left main disease or no obstructive CAD and ejection fraction will be based on diagnostic procedures performed prior to randomization and will not include information obtained from protocol-assigned catheterization procedures or core lab reviews of left ventricular angiography.

6.3. Core-lab determined ischemia population

The core-lab determined ischemia population is a subset of the ITT population. It consists of participants determined by the core lab to have moderate or severe ischemia on a pre-randomization imaging stress test or severe ischemia on a pre-randomization non-imaging exercise tolerance test (ETT). Hereafter in this document, “moderate or severe ischemia” refers collectively to moderate or severe ischemia by stress imaging or severe ischemia by non-imaging ETT.

6.4. Procedure-based populations

Safety analyses will be performed in subgroups of participants for whom the safety issue is relevant. Thus, complications of protocol-assigned CCTA, catheterization, PCI, and CABG procedures will be evaluated in the subset of participants undergoing these procedures. Only procedure-related complications are systematically collected. Complications of adjunctive therapies such as dual anti-platelet therapy are not systematically collected.

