9.3. Protocol-assigned catheterization in the INV group

Core-lab angiographic findings from the first post-randomization diagnostic catheterization procedure in participants assigned to INV will be summarized by the frequency distribution of the number of native vessels with at least 50% stenosis and the percentage of participants with at least 50% stenosis in specific locations (left anterior descending [LAD] disease, proximal LAD disease, circumflex disease, right coronary artery disease, left main disease). Summaries of native vessel stenosis will be presented for all participants and for the subset with no prior CABG. For participants with prior CABG, summaries will include the number vein or arterial grafts with \geq 70% stenosis and the number of arterial grafts with at least \geq 70% stenosis. Other scores summarizing the extent and/or severity of disease may be reported in supplemental analyses and reports.

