11.3.2. Non-use of discretionary catheterization and revascularization in CON

The CON strategy mandates non-use of catheterization or revascularization procedures except in the case of suspected acute events (acute coronary syndrome, resuscitated cardiac arrest, or acute ischemic heart failure) or unacceptable angina refractory to maximally tolerated medical therapy. Catheterization or revascularization performed for other reasons, such as physician or participant preference, is considered non-adherence. A pattern of frequent early discretionary catheterization or revascularization in CON participants, especially those without prior endpoint events, may attenuate the treatment effect and cloud the interpretation of the study's primary ITT analysis.

Two types of analyses will be performed for estimating the cumulative incidence of catheterization and revascularization in the CON group. The first type of analysis will ignore the occurrence and timing of clinical endpoint events. The second type of analysis will only consider catheterization and revascularization procedures performed before the participant's first primary clinical endpoint event. The latter analysis is of particular interest because procedures performed after the occurrence of a clinical endpoint event will not impact power or interpretation for analyses of that type of endpoint. Quantities to be estimated will include all or a subset of the following:

- Cumulative incidence of catheterization for any reason
 - All
 - Occurring before participant's first primary endpoint event
- Cumulative incidence of catheterization for a suspected acute event

- All
- Occurring before participant’s first primary endpoint event
- Cumulative incidence of catheterization for site-reported OMT failure/refractory angina
 - All
 - Occurring before participant’s first primary endpoint event
- Cumulative incidence of catheterization for any other reason (non-adherence)
 - All
 - Occurring before participant’s first primary endpoint event
- Cumulative incidence of revascularization for any reason
 - All
 - Occurring before participant’s first primary endpoint event
- Cumulative incidence of revascularization for a suspected acute event
 - All
 - Occurring before participant’s first primary endpoint event
- Cumulative incidence of revascularization for site-reported OMT failure/refractory angina
 - All
 - Occurring before participant’s first primary endpoint event

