Transitions occurring because of a suspected acute event or OMT failure may dilute power (because they occurred prior to a confirmed endpoint event) but are not violations of the CON strategy (because the strategy includes catheterizations performed in the case of a suspected acute event or OMT failure). Although these may dilute power, they do not necessarily reflect negatively on the study's conduct (because they are part of the treatment being studied).

An additional set of analyses will focus on estimating the underlying hazard rates of elective catheterization and elective revascularization in the CON group. The main goal is to shed light on the extent to which statistical power may be attenuated by catheterization or revascularization performed on a non-emergency basis in the CON group. Analysis will focus on estimating the underlying “intensity rates” of elective catheterization and revascularization (as opposed to the cumulative incidence function accounting for competing risks) because power calculations using multi-state models and accounting for treatment crossover typically require specification of such intensity rate parameters. Because the analysis focuses specifically on “elective catheterization” and “elective revascularization,” and to avoid counting catheterizations and revascularizations that may be true endpoint events, follow-up for these analyses will be censored 7 days prior to the participant’s first best-available composite endpoint event (death, myocardial infarction, hospitalization for unstable angina, hospitalization for heart failure, resuscitated cardiac arrest). The intensity rates of elective catheterization and elective revascularization will be estimated parametrically under an exponential and/or Weibull model and non-parametrically using a Nelson-Aalen type estimator. Because interpretable summary measures derived from the Nelson-Aalen estimator require the strong and arguably implausible assumption that elective catheterization and revascularization are independent of censoring and death, they will be regarded as informal and exploratory, and will be presented in the context of their inherent limitations.

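### SAP 6.4 confines procedural complications to an undefined class of protocol-assigned procedures among recipients, so complications that are not adjudicated endpoints have no summary per participant randomized to each strategy.

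*SAP*

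**What the plan says.** Section 6.4 of the SAP is the only place in the supplied text that describes an analysis of procedural complications. It says that "complications of protocol-assigned CCTA, catheterization, PCI, and CABG procedures will be evaluated in the subset of participants undergoing these procedures". It adds that "Only procedure-related complications are systematically collected", without limiting collection to one arm.

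The key term appears in two other places, neither of which defines it. Section 9.3 is headed "Protocol-assigned catheterization in the INV group" and deals with the first diagnostic catheterization after randomization in INV. Section 6.2 says that eligibility for the Protocol Version 2.0 population "will not include information obtained from protocol-assigned catheterization procedures", which separates such catheterizations from pre-randomization work-up.

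On CON, Section 4 notes that "the conservative strategy includes performance of catheterization after OMT failure". Section 11.3.2 says that "the strategy includes catheterizations performed in the case of a suspected acute event or OMT failure". The same section also states: "Catheterization or revascularization performed for other reasons, such as physician or participant preference, is considered non-adherence".

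**The concern.** The trial compares two strategies. The procedural cost of a strategy is the share of participants assigned to it who have a complication from any procedure it leads to. Section 6.4 gives a different quantity: risk among people who had a procedure of a certain class. Having a procedure is a post-randomization event, and the route to it differs by arm. INV calls for early catheterization (Section 11.3.1). CON reserves it for acute events or refractory angina, with some discretionary use expected (Section 11.3.2).

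Two things are at stake. First, two programmers could draw different analysis sets from 6.4 and both claim to follow it. Second, even with the term settled, risk among recipients does not tell a reader how many more participants have a procedural complication under INV, or how many have one under CON.

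**Working it through.** The plan has no figure to reproduce. The check sets the passages side by side.

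**Step 1. Which procedures does 6.4 cover?**

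| Post-randomization procedure | Relevant SAP text | Inside 6.4? |
|---|---|---|
| First INV catheterization and the revascularization that follows | 9.3, 11.3.1 | Yes |
| Repeat INV procedures | 9.3 covers only the first catheterization; nothing further stated | Depends on the reading |
| CON procedures for a suspected acute event or failure of medical therapy | Part of the strategy: 4, 11.3.2 | Depends on the reading |
| CON procedures for other reasons | Non-adherence: 11.3.2 | No, on any reading |

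**Step 2. Is there a summary by randomized arm elsewhere?** Section 11.3.2 estimates how often CON participants have catheterization and revascularization, by reason, but attaches no complication analysis. Sections 10.3, 10.8 and 10.9 compare or count CEC endpoints by arm: all-cause and cardiovascular death, MI, stroke, resuscitated cardiac arrest and heart-failure hospitalization. Section 10.1 groups Type 4a and 5 MIs as procedural, and 10.9 counts MI by type. Complications that are not CEC endpoints appear in none of these.

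**Step 3. Which quantity is missing?** For arm *a*, let *u* be the share of randomized participants who have a procedure and *c* the share of those with at least one complication. Burden per randomized participant is *u* × *c*. Section 6.4 gives *c* for protocol-assigned procedures only. Section 11.3 gives *u* for catheterization and revascularization. For CON, *c* is missing for discretionary procedures and uncertain for the rest, so the product cannot be formed.

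**Step 4. Scale.** From Section 4, 5,179 / 2 = 2,589.5, or about 2,590 per arm under 1:1 allocation. One percentage point is 2,590 × 0.01 ≈ 26 participants.

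The documents give neither *u* nor *c*. Purely as an illustration, assume *u* = 80% in INV and 20% to 25% in CON, and *c* = 3% to 4.5% in either arm:

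- INV: 0.80 × 3% = 2.4% to 0.80 × 4.5% = 3.6%.
- CON: 0.20 × 3% = 0.60% to 0.25 × 4.5% = 1.125%, or 2,590 × 0.0060 ≈ 16 to 2,590 × 0.01125 ≈ 29 participants.
- Difference: 2.4 − 1.125 = 1.275 points to 3.6 − 0.60 = 3.0 points, or about 33 to 78 participants per 2,590.

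Under these assumptions, 16 to 29 is an upper limit on the CON participants left out. It treats every CON procedure as excluded and takes no account of complications already counted as CEC endpoints.

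**The case against.** A reader might infer that harm cannot be compared between the strategies. The documents contradict that. Follow-up starts at randomization (Section 10.2), so adjudicated events around a procedure count in both arms. The secondary endpoints and the net-clinical-benefit composites with stroke (Section 3) carry the serious harms, and all-cause mortality is compared at interim looks (Section 11.4). This part of the defence stands, with one small limit: the by-type MI counts in 10.9 take only each participant's first MI, so a procedural MI after an earlier MI is not in that table.

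A reader might also infer from 9.3 that all CON procedures are excluded. That is one plausible reading, not a stated rule. The 9.3 heading adds the arm, which would be unnecessary if the term already meant INV. Section 6.4 applies the term to CCTA, which Sections 6.1 and 6.2 treat mainly as a pre-randomization test and which belongs to neither arm. Catheterization for an acute event or failure of medical therapy is part of CON.

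Risk among recipients is a standard descriptive safety measure. Section 6 reserves intention-to-treat for major treatment comparisons, and 6.4 describes none, so the two sections do not conflict. That also stands: the recipient summary is useful and should stay, but it does not answer the strategy-level question.

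Lastly, the full protocol, the SAP Appendix for Definitions and Reporting Conventions and the CEC Charter were not among the supplied documents. Any of them may define the term or specify a safety table. The finding is limited to the text at hand.

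**Conclusion.** The point holds in a limited form. The only described analysis of procedural complications uses an undefined class of procedures and a denominator fixed after randomization. Discretionary CON procedures are certainly outside it; strategy-consistent CON procedures and repeat INV procedures may be. For complications that are not CEC endpoints, no burden per assigned participant can be obtained from the plan as written.

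No primary or secondary endpoint inference changes. The numerical size is unknown, because the illustration in the working rests wholly on assumed rates. The omission itself does not depend on those rates. It matters because procedural burden by assigned strategy is something a reader of an invasive-versus-conservative trial will expect to find.

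**What to change.** In Section 6.4:

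1. For catheterization, PCI and CABG, replace *protocol-assigned* with *all post-randomization*. If a definition exists in an appendix or the full protocol, cite it and reconcile it with this wording.
2. Keep the per-procedure summary among recipients, and present it by arm and indication. Section 11.3.2 shows that site-reported indications for catheterization are already captured on the e-CRF.
3. Add a table in the intention-to-treat population: for each arm, the number and proportion of randomized participants with at least one procedural complication, with the risk difference and 95% CI. Label it descriptive, and show which complications are also CEC endpoints so that they are not read as additional harm.
4. Report CCTA complications separately.

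The cost is a wording change and one more table. Section 6.4 does not restrict collection by arm, but it does not state that unplanned CON procedures are covered as fully as planned INV ones. Completeness in CON should be checked and footnoted. If those data turn out not to have been collected, the table must say so.
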